1.6 Dose Rationale

In this study, the indocyanine green dose began at 5 mg/kg, aligned with previous nonclinical and clinical experience at the University of Pennsylvania. Given the incidence of HTN in our CNS cohort and seeking optimal signal to background ratio, we decreased to 2.5 mg/kg to assess efficacy and safety. Thus, we intend to evaluate dose ranges but will not exceed 5mg/kg. Alternately, based on neurosurgeon plan, patients may receive a 25 mg bolus of ICG at the time of induction administered intravenously by the anesthesiologist. This 25 mg dose of indocyanine green is similar to dosing for other intraoperative vascular visualization. This can cause less usage of the drug, lower risk of adverse event occurrences.

We make no changes to the route of administration.. The most important difference between what is labeled on the package and this protocol is the dose regimen (up to 5 mg/kg) and the amount of time elapsing before intraoperative imaging begins (up to 72 hours). This protocol began with 24-hour infusions the day before surgery based on previous nonclinical and clinical experience at the University of Pennsylvania. Interested in strength of signal to background ratio over extended or shortened timeframes, we allow for a range of up to 72 hours. The rationale for dosing timing prior to surgical intervention is based on the minimal risks with indocyanine exposure, to accommodate logistical scheduling of surgeries, and to collect data on optimal signal to background ratio in various tumor types.

Indocyanine green has been used in a dose-escalation trial up to a maximum dose of 10 mg/kg [\[22\]](#) and in other trials 3-5 mg/kg [\[13, 17-21\]](#). Indocyanine green has a LD₅₀ after IV administration of 50 to 75 mg/kg [\[22\]](#).

As [name] and other researchers have used an IV injection of indocyanine green to obtain imaging sufficient to describe discrepancies in the structure of abnormal hyper-vascularized tissue [\[47\]](#), it therefore stands to reason that we would be able to accomplish our objective of imaging tumors with indocyanine green using a similar dose.

CONFIDENTIAL

This material is the property of the University of Pennsylvania.

Interim data analysis (see [Section 7.2](#)), specifically the fluorescence signal to background ratio, will determine the optimal timing of indocyanine green infusion, which will guide future infusion in this protocol and future protocols.

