1.7 Risk/Benefit Assessment

1.7.1 Known Potential Risks

Risks of Indocyanine Green:

The risks of using indocyanine green are well described and exceedingly rare [15, 28]. Indocyanine green is known to have a rare but serious side effect known as anaphylaxis and because of this, patients with a history of iodide allergies will not be considered candidates in this study. There is no connection with any other particular contrast agent or drug or food allergy. Anaphylaxis is an allergic reaction to a substance that can cause swelling of the skin, shortness of breath, dizziness, increased heart rate (HR), rash, and/or death. The indocyanine green dye will be administered in a procedure room with trained nurses who will closely monitor the subject's vital signs (HR, blood pressure [BP], oxygen level [pulse oximetry], and skin color) to check for any signs of anaphylaxis. In the event of an anaphylactic reaction, the indocyanine green injection will be stopped and medication will be used to control the reaction. One study placed the rate of adverse reactions for indocyanine green injections at fewer than 4 in 240,000 [29].

Adverse Events (as of January 2019):

The AEs table below outlines the number of events that occurred by Common Terminology Criteria for Adverse Events (CTCAE) v4.0 event category in this protocol as of January 2019. Subjects could have had more than one AE. Of 296 infusions, there were 55 total AEs observed in 35 patients: 36 events in the 5 mg/kg dose cohort and 19 events in the 2.5 mg/kg dose cohort. Out of the 55 AEs, one was a serious adverse event (SAE) (HTN). One patient experienced two unique AEs during infusion (HTN-General Disorder).

Overall, in 296 patients, HTN accounted for 5.7% of AEs; mild arm pain/discomfort accounted for 7.4% of AEs, general disorders accounted for 2.7%, administration site conditions accounted for 2% of AEs and 0.6% patients reported a gastrointestinal issue.

Of the patients in the **5 mg/kg dose cohort**, 5.4% reported vascular disorders, 9.1% reported mild arm discomfort or pain, 3.2% had general disorders and 1.6% had administration site conditions.

Of the patients in the **2.5 mg/kg dose cohort**, 6.4% reported vascular AEs, 4.6% of them had mild arm discomfort or pain, 1.8% had general disorders, 2.7% had administration site conditions and 1.8% had gastrointestinal AEs.

CONFIDENTIAL

This material is the property of the University of Pennsylvania.

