3.3 Secondary Study Endpoints

The secondary end-point of the study is to identify based on signal to background noise the optimal timing for surgery following infusion of indocyanine green and dose for optimal safety without toxicity for visualization of indocyanine green during intraoperative imaging in nervous system tumors.

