5.1.2 Treatment Regimen

The dose is a single infusion of up to 5 mg/kg reconstituted indocyanine green injected intravenously in the dark, within 72 hours of the operation. Alternately, subjects may receive a 25 mg dose of indocyanine green administered by the anesthesiology team during induction. If subjects experience any AEs, please reference [Section 8.2](#) for protocol intervention. There is no second dose.

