6.2 Visit 2 (CTRC, Infusion visit within 72 hours before operation)

For subjects receiving ICG with 72 hours of surgery, they will arrive at the Perelman Center for Advanced Medicine Clinical & Translational Research Center, [name] or the ACC, Farm Journal Building at PAH, [name], or the ACC at PPMC, [name] for their infusions at their respective infusion locations within 72 hours prior to the scheduled surgery to receive their injection of indocyanine green by trained nursing staff. The nursing staff places a peripheral IV and calls the pharmacy for the scheduled infusion of up to 5 mg/kg of indocyanine green diluted in sterile water administered intravenously in the dark, over 40 minutes. The nurse monitors subjects pre infusion, during the 40-minute infusion and for 30 minutes post infusion for any signs of anaphylaxis. For all AEs and prescribed treatment, please see **Section 6.5** and **8.2** Expected Adverse Events and Treatment).

During the study visit, subjects' vital signs are monitored as follows: pre infusion; then at 5 minutes after infusion starts, then at every 15 minutes over the 40-60 minute infusion time frame. During the post infusion 30 minute observation period, vital signs are completed at 10-minute intervals and the subject is monitored for any signs of anaphylaxis. The following vital signs are monitored and recorded during each time point: HR, BP, skin color, and oxygen levels (pulse oximetry) and the subject is observed for any adverse sign or symptoms that could include but is not limited to HTN, mild pain or discomfort at infusion site and signs of anaphylaxis. Symptoms are treated according to prescribed interventions outlined in the ICG Treatment Plan.

The Neurosurgeon may want to compare both indocyanine green with other Standard of Care NIR dyes (ex: 5-ALA) intra-operatively to see which dye localizes more accurately and precisely at the region of interest. This may result in using more than one dye for your surgery.

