6.3 Visit 3: Operative Visit

Patients will come to one of the University of Pennsylvania Health System hospitals to undergo removal of their tumor as clinically indicated. Surgical approach and exposure are performed according to standard of care. The entire procedure is photo-documented and recorded as per standard of care. There are five phases of NIR imaging; however, one or more of the phases may be omitted. Patients receiving intra-op ICG by anesthesia will report day of surgery and not have an infusion suite visit.

CONFIDENTIAL

This material is the property of the University of Pennsylvania.

Dura View: upon opening the skull at the level of the dura but prior to opening the dura, a brief view of the dura is obtained with the NIR imaging system – Dura View.

Cortex View: upon opening the dura but prior to violating the cortex of the brain, another brief view of the cortex is with the NIR imaging system – Cortex View.

Tumor View: Prior to initial resection but upon identification of the tumor, the NIR imaging system (i.e. VS₃ Iridium, Stryker 1588 AIM) is used to visualize the tumor in its native and untouched form. The lights in the OR are turned off and the infrared imaging system is turned on. The video screen displays the images of the tumor area, and the surgeon measures the spectral reading from the tumor. The imaging system captures the infrared signal that is emitted from the indocyanine green that has been taken up by the tumors. Initial tumor fluorescence will be recorded and visualized. After initial visualization, surgical resection will proceed as per standard of care. A NIR microscope (i.e. Leica FL800, Zeiss INFRARED™ 800) will be used to assist with the surgical resection.

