8.4 Reporting of Serious Adverse Events (SAEs) and Unanticipated Problems

Reporting period

Adverse events are reported from the time of informed consent until study completion. For this study, study completion is defined as the conclusion of surgery.

Investigator reporting:

Every SAE, regardless of suspected causality (e.g., relationship to study drug(s) or study procedure or disease progression) is reported to the Pharmacovigilance Officer within **24 hours** of learning of its occurrence.

Recurrent episodes, complications, or progression of the initial SAE is reported as the follow-up to the original episode within 24 hours of the investigator receiving the follow-up information. An SAE considered completely unrelated to a previously reported one is reported separately as a new event.

Send the notification (MedWatch or CIOMS form) to the Pharmacovigilance Officer.

New information regarding the SAE is reported as it becomes available and in the same manner that the initial SAE (i.e. MedWatch or CIOMS). The investigator follows the event to resolution or until the event is deemed and documented irreversible, whichever is longer.

Investigator Reporting: Local Reporting Requirements

The investigator reports AEs and SAEs to his/her IRB of record and other local regulatory groups per the local requirements.

8.5 Reporting Serious Adverse Events (SAEs) to the Data Safety Monitoring Committee (DSMC) at the Local PI site

The following are reported to the DSMC:

- All **SAEs** defined as reportable in the protocol.
- All AEs grade 3 or higher within 10 days of knowledge.
- All unexpected deaths within 24 hours of knowledge.
- All other deaths within 30 days of knowledge.

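### Adverse events are observed differently after the 25 mg induction dose and after awake mg/kg infusions, so their overall rates should not be compared

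*Combined protocol and SAP*

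**What the plan says.** All references are to the combined protocol and SAP.

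- **Two regimens.** Section 5.1.2 gives a single infusion of up to 5 mg/kg before surgery, or alternatively "subjects may receive a 25 mg dose of indocyanine green administered by the anesthesiology team during induction".
- **Expected safety of the smaller dose.** Section 1.6 says: "This can cause less usage of the drug, lower risk of adverse event occurrences".
- **Use of safety data.** Section 3.3 seeks the "dose for optimal safety without toxicity for visualization of indocyanine green during intraoperative imaging in nervous system tumors". Section 7.2 uses descriptive signal and safety data, by tumor type, to settle dosing and timing. Neither section excludes the 25 mg regimen.
- **Observation of mg/kg infusions.** Section 6.2 has a nurse watch the subject before the infusion, "during the 40-minute infusion and for 30 minutes post infusion for any signs of anaphylaxis". It adds timed vital signs and a watch for pain or discomfort at the infusion site.
- **Observation of the 25 mg dose.** Section 6.3 says: "Patients receiving intra-op ICG by anesthesia will report day of surgery and not have an infusion suite visit". After screening, Table 2b marks AE collection at the operative visit only.
- **Reporting window.** Section 8.4 says: "Adverse events are reported from the time of informed consent until study completion". It continues: "For this study, study completion is defined as the conclusion of surgery".

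**The concern.** The reporting window has the same formal end under both regimens, but its content differs. A subject given a mg/kg infusion is awake for the dose, for the observation period and for the time up to surgery, and can report pain, headache, itching or nausea. A subject dosed at induction is anaesthetised from the dose until the window closes. No section adds solicited AE collection after waking.

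If the two sets of AE rates are placed side by side to choose a dose, the induction regimen may show fewer events because fewer could be noticed. Such a result would appear to bear out the expectation in section 1.6 whether or not it is true. The secondary conclusion on dosing is at stake. The primary endpoint, diagnostic accuracy against histopathology, is not touched.

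**Working it through.** **1. Reproduce the plan's AE counts.** Inputs are the group sizes in section 1.5 (186 at 5 mg/kg, 110 at 2.5 mg/kg, 296 in all) and the category percentages in section 1.7.1. Count = percentage × group size, rounded.

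| Category | 5 mg/kg (186) | 2.5 mg/kg (110) | Both (296) |
|---|---|---|---|
| Hypertension/vascular | 5.4% → 10 | 6.4% → 7 | 17 (5.7%) |
| Arm pain or discomfort | 9.1% → 17 | 4.6% → 5 | 22 (7.4%) |
| General disorders | 3.2% → 6 | 1.8% → 2 | 8 (2.7%) |
| Administration site | 1.6% → 3 | 2.7% → 3 | 6 (2.0%) |
| Gastrointestinal | none given → 0 | 1.8% → 2 | 2 (0.68%; printed 0.6%) |
| Total | 36 | 19 | 55 |

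The totals of 36, 19 and 55 match section 1.7.1. That section's pooled sentence says "mild arm pain/discomfort accounted for 7.4% of AEs", but the denominator is the 296 infused patients: 22/296 = 7.4%, whereas 22/55 = 40%. The shares below therefore use the counts.

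**2. Sort the categories by how they are noticed.** Section 8.2 describes general disorders through itching, headache, fatigue and similar complaints. Gastrointestinal events are nausea. Site conditions are tenderness or spasm, with extravasation as the visible exception.

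- Arm pain + general + gastrointestinal: 22 + 8 + 2 = 32; 32/55 = 58%.
- Adding all site conditions: 32 + 6 = 38; 38/55 = 69%.
- Narrowest reading, with general disorders and site conditions all treated as visible: 22 + 2 = 24; 24/55 = 44%.

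**3. The remaining category.** The 17 hypertension events can be measured in theatre. Blood pressure after induction also reflects the anaesthetic, so these events are observable under both regimens but not on equal terms.

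**4. Awake observation inside the window.** For mg/kg infusions, section 6.2 gives 40 to 60 minutes of infusion plus 30 minutes afterwards, that is 70 to 90 minutes from the start, followed by the time to surgery. For 25 mg at induction there is essentially none.

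**5. What the existing data say about 25 mg.** All 296 infused subjects received 2.5 or 5 mg/kg, so the documents hold no trial AE data for the induction regimen.

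**The case against.** The strongest reply is that no such comparison is clearly planned. The Study Summary (Part IIb) and section 2 confine dose optimisation to second-window dosing, which the objectives describe as high-dose and delayed; a 25 mg dose at induction is neither. The interim groups in section 7.2 are 2.5 and 5 mg/kg, section 1.6 bases optimal timing on the signal-to-background ratio, and section 7.4 calls the analyses mainly descriptive. This stands as a limit: the problem arises only if 25 mg rates are set beside the others. It does not remove the point, because the wording of sections 3.3 and 7.2 leaves that open.

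Three stronger readings are tempting, and the documents do not support them.

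- **A reader might infer that symptom AEs after induction dosing can never be reported.** Section 8.1 has subjects told to report later events they think related, so late reports are possible, though unsolicited and outside the section 8.4 window. Table 2b also requires vital signs and AE recording at the operative visit.
- **A reader might infer that 58% to 69% is the false reduction to expect.** That would need the same true rate and event mix for a much smaller dose given differently. The trial's own arm-pain figures differ by dose (9.1% against 4.6%). The counts are events, not patients: the 55 events arose in 35 patients (35/296 = 11.8%). The AE table announced in section 1.7.1 was not available for this check, so the sorting rests on section 8.2.
- **A reader might infer that the 25 mg regimen must look safer whatever the truth, or that section 1.6 asserts a result.** Section 1.6 says only that risk can be lower. A smaller dose may truly cause fewer events, and some brief infusion symptoms may not occur at all in an anaesthetised patient.

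**Conclusion.** The concern holds in a conditional form. AE ascertainment differs between the two regimens. If 25 mg AE rates are compared with mg/kg rates under sections 3.3 and 7.2, a lower recorded rate could not be separated from lost observation. About 32 to 38 of the 55 AEs recorded to January 2019 (58% to 69%; 44% on the narrowest reading) were in categories that depend mainly on an awake patient. This is the share of past events at stake, not an estimate of bias. The comparison of 2.5 with 5 mg/kg is unaffected, because both are given as awake infusions with the same monitoring.

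The conclusion assumes that patients stay anaesthetised from induction to the end of surgery and that section 8.2 fairly describes the events counted in section 1.7.1. It is a modest, inexpensive improvement to a secondary analysis.

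**What to change.** **Section 7.2**

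- Report safety of the 25 mg induction regimen on its own denominator.
- Limit any safety comparison between induction and pre-operative dosing to events observable in both settings, such as anaphylaxis or urticaria and extravasation. Include hypertension only if it is flagged as confounded by anaesthesia.
- State that symptom AEs are not comparably ascertained under the two regimens.

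**Section 1.6**

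- Mark the lower AE risk of 25 mg as an expectation based on dose, which this study's overall AE rates cannot confirm.

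**Cost.** Wording in two sections and one extra split in the safety table. No dose, schedule or clinical rule changes. The change adds no new AE information for the 25 mg regimen, and the investigators give up any overall AE-rate comparison across the two routes.

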1.7 Risk/Benefit Assessment

1.7.1 Known Potential Risks

Risks of Indocyanine Green:

The risks of using indocyanine green are well described and exceedingly rare [15, 28]. Indocyanine green is known to have a rare but serious side effect known as anaphylaxis and because of this, patients with a history of iodide allergies will not be considered candidates in this study. There is no connection with any other particular contrast agent or drug or food allergy. Anaphylaxis is an allergic reaction to a substance that can cause swelling of the skin, shortness of breath, dizziness, increased heart rate (HR), rash, and/or death. The indocyanine green dye will be administered in a procedure room with trained nurses who will closely monitor the subject's vital signs (HR, blood pressure [BP], oxygen level [pulse oximetry], and skin color) to check for any signs of anaphylaxis. In the event of an anaphylactic reaction, the indocyanine green injection will be stopped and medication will be used to control the reaction. One study placed the rate of adverse reactions for indocyanine green injections at fewer than 4 in 240,000 [29].

Adverse Events (as of January 2019):

The AEs table below outlines the number of events that occurred by Common Terminology Criteria for Adverse Events (CTCAE) v4.0 event category in this protocol as of January 2019. Subjects could have had more than one AE. Of 296 infusions, there were 55 total AEs observed in 35 patients: 36 events in the 5 mg/kg dose cohort and 19 events in the 2.5 mg/kg dose cohort. Out of the 55 AEs, one was a serious adverse event (SAE) (HTN). One patient experienced two unique AEs during infusion (HTN-General Disorder).

Overall, in 296 patients, HTN accounted for 5.7% of AEs; mild arm pain/discomfort accounted for 7.4% of AEs, general disorders accounted for 2.7%, administration site conditions accounted for 2% of AEs and 0.6% patients reported a gastrointestinal issue.

Of the patients in the **5 mg/kg dose cohort**, 5.4% reported vascular disorders, 9.1% reported mild arm discomfort or pain, 3.2% had general disorders and 1.6% had administration site conditions.

Of the patients in the **2.5 mg/kg dose cohort**, 6.4% reported vascular AEs, 4.6% of them had mild arm discomfort or pain, 1.8% had general disorders, 2.7% had administration site conditions and 1.8% had gastrointestinal AEs.

CONFIDENTIAL

This material is the property of the University of Pennsylvania.

- Adverse reactions occurring in < 1% of patients in the first 6 weeks after surgery were: chills, photosensitivity reaction, solar dermatitis, hypotension, abnormal liver function test, and diarrhea.

CONFIDENTIAL

- Neurologic events related to the surgical procedure occurred in 29% of patients and included: aphasia, hemiparesis, hemianopia, headache, seizure, hemiplegia, monoparesis, hypoesthesia, and brain edema.
- Elevated liver enzymes occurred in clinical studies.

There are no anticipated risks of dosing of simultaneous dosing of Indocyanine green and 5-ALA.

Risks of the Use of NIR Imaging Systems:

The video images that we will take intraoperatively may result in the surgeon changing the operation. He/she will not change the scale of the operation to do anything that was not described to the subject during the surgical consent process beforehand. The possible risks associated with taking these images are as follows:

- There is a chance that an area without any cancer in it will glow in the video images. If that happens, the surgeon may remove healthy tissue that did not need to be removed and that would not have been removed in a standard surgery.
- There is a chance that while removing additional tissue that glows in the video images, the subject could be put at an increased risk of having a surgical complication. A surgical complication includes, but is not limited to bleeding, infection, pain, injury to a major organ, nerve damage, blood clot in the arms/legs/other region of the body, and/or death.
- There is a chance that being under anesthesia for the extra 15-20 minutes that it takes to obtain the images for this study could put the subject at an increased risk of having of a common side effect associated with anesthesia. These common side effects include, but are not limited to nausea and vomiting after surgery, sore throat and hoarseness, shivering/chills, confusion, increased BP, and/or muscle aches.
- Finally, there is a chance that the imaging technique could falsely reassure the surgeon that all of the cancer has been taken out, so not as much tissue will be removed. In other words, not all of the cancer could be taken out.

Oncologic surgery in the brain is always balanced by the potential neurologic/functional risks of additional resection, and for this reason neurosurgeons are always weighing the risks and benefits of additional tumor resection. The addition of the fluorescent dye does not change the calculus for the treating physician/neurosurgeon. The surgeon will continue to weigh the risks and minimize these risks. If he/she thinks that removing the extra tissue is too risky, they will not remove the extra tissue. If removal of additional tissue has minimal risk, the surgeon may choose to remove the additional tissue for diagnostic test considerations.

CONFIDENTIAL

This material is the property of the University of Pennsylvania.

